Mean # of injections per subject in 12 months prior to baseline	% (n/N)
Mean # of injections per subject in 12 months prior to 5+ year post treatment visit	% (n/N)
Time to first injection for low back pain in same location post Intracept Procedure	Mean + SD, Median, Range

	CD_3012_Rev B Five-Plus Year Follow-Up of SMART Trial Statistical Analysis Plan	Date Effective: November 5, 2019 Page 18 of 21
---	--	---

Table 13 – Surgical Interventions	
	SMART 5+ Yr Follow-up Subjects N = XX
Number (%) of subject reporting a procedure	% (n/N)
Number of procedures	% (n/N)
Re-intervention Rate over Time	
1 Year	S% (95% CI)
2 Year	S% (95% CI)
5 Year	S% (95% CI)
Type of procedure:	
Discectomy	% (n/N)
Lumbar fusion	% (n/N)
RF Ablation	% (n/N)
Other	% (n/N)
At the same level of Intracept treatment?	
Yes	% (n/N)
No	% (n/N)
Time to intervention (post Intracept procedure)	Mean + SD, Median, Range
Same etiology and level as Intracept treatment	Mean + SD, Median, Range
Different etiology or level from Intracept treatment	Mean + SD, Median, Range

Table 14 – Pain Status at 5 + Years	
	SMART 5+ Yr Follow-up Subjects N = XX
Pain Status	
Constant	% (n/N)
Intermittent	% (n/N)
No Pain	% (n/N)
Experiencing Pain	
Same location as prior to Intracept Procedure	% (n/N)
Different location from prior to Intracept Procedure	% (n/N)
Same nature as prior to Intracept Procedure	% (n/N)
Different nature from prior to Intracept Procedure	% (n/N)
Time (per year) effect on VAS in INTRACEPT group	Mean, N, 95% CI, rm F-test p (Ho: time=0)

	CD_3012_Rev B Five-Plus Year Follow-Up of SMART Trial Statistical Analysis Plan	Date Effective: November 5, 2019 Page 19 of 21
---	--	---

Table 15 – Durability at 5 + Years	
	SMART 5+ Yr Follow-up Subjects N = XX
Number (%) of subjects reporting a re-intervention (lumbar procedure adjudicated as same location and etiology as Intracept procedure)	% (n/N)
Number (%) of subjects reporting actively using opioids (defined as > 25% of total prescribed dosage in 30 days prior to visit)	%(n/N)
Number (%) of subjects reporting low back pain injections in same treatment location as Intracept.	% (n/N)
Number (%) of subjects reporting less than 2 point decrease in pain (in same location) compared to baseline	% (n/N)
Number (%) of subjects reporting less than 10 point decrease in ODI compared to baseline	% (n/N)

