Number (%) of subjects reporting at least one of the above	% (n/N)
Intracept therapy success rate at 5 plus years (none of the below criteria are met)	% (n/N)

The following is the definition of therapy success:
 
 
a. ODI decrease of 10 or more at 5+ years
 
b. VAS decrease of 2 or more at 5 + years
 
c. No procedures since the Intracept procedure (that is adjudicated as treatment failure due to same location, same etiology, same severity as baseline)
 
d. No injections (in past 12 months and adjudicated as for same location, etiology, severity as baseline)
 
e. Not actively taking opioids (defined as > 25% of total dosage in 30 days prior to study visit)
 
	

	CD_3012_Rev B Five-Plus Year Follow-Up of SMART Trial Statistical Analysis Plan	Date Effective: November 5, 2019 Page 20 of 21
---	---	--

Table 16 – Patient Satisfaction	
	Subject Frequency
How do you feel your condition is post the Intracept Procedure?	
Improved	% (n/N)
Slightly	% (n/N)
Much	% (n/N)
Vastly	% (n/N)
No Change	% (n/N)
Worsened	% (n/N)
Slightly	% (n/N)
Much	% (n/N)
Vastly	% (n/N)
I am satisfied with the results of my surgery	
Yes	% (n/N)
No	% (n/N)
All things considered; I would have the surgery again for the same condition	
Yes	% (n/N)
No	% (n/N)
Were you able to resume the activity level you enjoyed prior to onset of your low back pain?	
Yes	% (n/N)
No	% (n/N)

	CD_3012_Rev B Five-Plus Year Follow-Up of SMART Trial Statistical Analysis Plan	Date Effective: November 5, 2019 Page 21 of 21
---	--	---

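### SAP Table 15 does not report the composite defined in SAP 3.1.2: the success row is mis-worded, three failure rows are not complements of the definition, and the severity wording is inconsistent

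*SAP*

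**What the plan says.** SAP 3.1.2 lists a composite of five conditions: an ODI decrease of at least 10; a pain-score decrease of at least 2; no active opioid use for low back pain; no procedure adjudicated as treatment failure; and no injection in the past 12 months adjudicated as matching the baseline pain. The last two are both tied to location, etiology and severity. SAP 4.4.3.4 takes the success rate as the proportion of subjects who meet this composite.

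SAP Appendix A, Table 15 is the shell that reports it. It has five failure rows, then "Number (%) of subjects reporting at least one of the above", then "Intracept therapy success rate at 5 plus years (none of the below criteria are met". Beneath that stands a list a–e, introduced by "The following is the definition of therapy success", which repeats the conditions of 3.1.2. Four failure rows matter here:

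- Procedures: "lumbar procedure adjudicated as same location and etiology as Intracept procedure".
- Injections: "Number (%) of subjects reporting low back pain injections in same treatment location as Intracept".
- Pain: "reporting less than 2 point decrease in pain (in same location) compared to baseline".
- Opioids: a threshold of more than "25% of total prescribed dosage in 30 days prior to visit". The composite in 3.1.2 and item e of the list do not contain the word for prescribed.

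SAP 2.6 sets the adjudication categories. Treatment failure covers ongoing or worsened pain that is similar to the earlier pain in location, etiology and nature or severity. Pain that differs in any of these is classed as not related.

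**The concern.** Table 15 is where the study's only composite success rate will appear. Followed as printed, its success row selects subjects who satisfy none of the success conditions. That is easily seen to be unintended. The harder problem is that correcting the label does not settle the number. One repair points down to list a–e and the other points up to the failure rows, and the two sets do not describe the same subjects. Beneath both lies an adjudication rule whose severity wording differs between sections.

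At stake is whether one pre-specified table yields one rate. As written, the failure and success rows need not add up, and the choice between repairs could be made after the data are seen.

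**Working it through.** The documents give no target figure for this composite, so there is nothing to reproduce. The check is logical.

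**Step 1: definition against failure rows.**

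| Component | Definition (3.1.2, list a–e) | Failure row in Table 15 | Exact complement? |
|---|---|---|---|
| ODI | decrease of 10 or more | decrease under 10 | yes |
| Pain | decrease of 2 or more, no location condition | decrease under 2, and same location | no |
| Procedure | none adjudicated as failure on location, etiology and severity | adjudicated on location and etiology | no: severity missing |
| Injection | none adjudicated as matching on location, etiology and severity | reported, same location | no: adjudicated etiology and severity missing |
| Opioids | over 25% of total dosage | over 25% of prescribed dosage | wording differs |

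**Step 2: the label.** Five conditions, each met or not, give 2^5 = 32 patterns. The definition selects one (all met). The printed label selects one (none met). They do not overlap.

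**Step 3: do the two repairs agree?** Describe a subject by ODI met or not, pain decrease met or not, pain location same or different, and opioids active or not. Add four procedure classes (none; same location, etiology and severity; same location and etiology but different severity; other) and four injection classes (none; full match; same location but different etiology or severity; other). That is 2 × 2 × 2 × 2 × 4 × 4 = 256 states. The opioid rows are treated as equivalent.

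- Success by a–e requires ODI met, pain met and no active opioids, with 3 permitted procedure classes, 3 permitted injection classes and either pain location: 3 × 3 × 2 = 18 states.
- Of these, no failure row is triggered with 2 procedure classes, 2 injection classes and either location: 2 × 2 × 2 = 8. The other 18 − 8 = 10 are successes by definition yet counted as failures by the rows.
- Failing a–e while triggering no row: pain not met but in a different location, all else clear: 2 × 2 = 4 states.
- The remainder, 256 − 8 − 10 − 4 = 234, are failures on both.

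Reading the label as all of the conditions below gives 18 success states. Reading it as none of the rows above gives 8 + 4 = 12. They disagree in 10 + 4 = 14 of 256. These counts show the logic; they do not estimate how many subjects are affected.

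**Step 4: concrete cases.** A subject whose pain fell by less than 2, whose pain is in a different location, and who meets everything else is in neither row. A subject with a same-location injection adjudicated to a different etiology, and all else met, is in both.

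**Step 5: severity.** SAP 2.6 names worsened pain as failure, yet asks for similar nature or severity and calls different nature or severity not related. SAP 3.1.2 and list a–e ask for the same severity as at baseline. The Table 15 procedure row does not mention severity.

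**Step 6: effect per subject.** One reclassified subject moves the rate by 100/n points: 100/133 = 0.75 if all 133 subjects in SAP 2.1 take part (100/132 = 0.76 with the N in Table 1), and 100/66 = 1.5 at an assumed participation of about half.

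**The case against.** The strongest reply is that the endpoint is properly defined and only a table shell is loose. Much of that stands.

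- **The label.** A reader might infer that the study will count treatment failures as successes. The documents do not support this: 3.1.2 gives the composite in full and 4.4.3.4 counts those who meet it, so the intention is recoverable.
- **Injections.** A reader might infer that injections go unadjudicated, or that the row reaches back beyond 12 months. Neither follows. SAP 2.6 covers injections as well as procedures, and SAP 2.5 collects injections for the past 12 months only. What remains is that the row is worded on reported location while the definition uses the adjudicated result.
- **Pain location.** Since the pain item asks about the low back, the location phrase could merely mean the low back. That reading would match item b. But Table 14 separately tabulates "Different location from prior to Intracept Procedure", so the narrower filter can be programmed, and Table 15 does not exclude it.
- **Severity for procedures.** The procedure condition invokes the treatment-failure category, and 2.6 expressly puts worsened pain there. The severity phrase may be shorthand for that category, so the ambiguity is narrower than the bare wording suggests. Granting this and removing the different-severity procedure class still leaves 2 × 3 × 2 = 12 success states, of which 8 trigger no row and 4 do, plus the 4 unflagged failures. The mismatch survives. The injection condition does not use the treatment-failure category, so its ambiguity is greater.

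**Conclusion.** The point holds as a defect of reporting and adjudication wording. Table 15 does not report the composite of 3.1.2, and correcting the success label alone would not make it do so, because the procedure, injection and pain rows differ from the definition. The severity wording across 2.6, 3.1.2 and Table 15 also needs to be reconciled, most of all for injections.

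Size and direction cannot be determined from the documents. They depend on how many subjects have pain in a new location, same-site injections of another etiology, or interventions for worsened pain. The effect is 1/n per such subject, about 0.75 points at n = 133 and more with lower participation.

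A reader might infer that the main conclusion is at risk. It is not: the composite is a descriptive secondary endpoint, absent from the list in Protocol 5.2, Table 15 specifies no test for it, and the primary ODI analysis does not use it.

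**What to change.** In this order, before adjudication and analysis:

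1. Reconcile the severity wording in SAP 2.6, SAP 3.1.2 and Table 15, so that worsened pain of the same location and etiology is classified one way throughout. Which way is for the sponsor to decide.
2. State that the reconciled 3.1.2 definition governs Table 15.
3. Change the success row to say that all of the criteria below are met.
4. Rewrite the procedure, injection and pain failure rows as exact complements of the definition. Among subjects with every component observed, the any-failure and success rows then add to that number.
5. Because SAP 4.1 and 4.4.3 use observed data without imputation, report on a separate line the subjects whose missing component prevents classification.
6. Use one wording for the opioid denominator throughout.

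The cost is SAP wording and no new data collection. If adjudication has already begun, affected cases may need re-review, and the reported rate may move in either direction.

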4 PROTOCOL

This study entails contacting original SMART trial treatment arm subjects to seek participation in a data collection of current pain, functional status, and recent treatments. The study will be overseen at each participating study site by a primary investigator and clinical research coordinator (CRC). Telephone visits and data collection will be conducted by an independent study-wide clinical research nurse (CRN).

Five-Plus Year Follow-up Visit

Study subjects who were randomized to the treatment arm and received treatment in the original SMART trial are eligible to participate in this 5+ year follow-up data collection. Each study site will make initial contact with the prior study patient and discuss the SMART 5+ year data collection and discern if the prior subject is interested in participating. Informed consent will be obtained, and the same unique subject ID # used in the SMART trial will be assigned to the subject. Study participant logs will include subject ID, date(s) of contact, and date of consent/decline to participate and will be maintained by the study site and independent CRN.

Upon subject agreement to participate in the study, the CRC will forward subject contact information to the independent CRN who will then ensure informed consent and schedule the telephone study visit. The independent CRN will perform the telephone study visit and will be responsible for collection of all data elements on source document worksheets

including administering a verbal ODI-based questionnaire, collecting a numeric rating of low back pain over the past 7 days, an assessment of narcotic medications for low back pain taken in the past 30 days, injections for low back pain in the last 12 months, and surgical interventions since the subject's Intracept Procedure, and patient satisfaction with the Intracept Procedure. The independent CRN will enter all data elements into the clinical database.

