5.2 Secondary Effectiveness Endpoint

Secondary effectiveness endpoints are:

- a) The mean reduction from baseline in patient reported pain.
- b) Responder rates for ODI - proportion of subjects who achieve \geq 10-point reduction in ODI from baseline to 5+ years post-treatment.
- c) Responder rates for pain rating - proportion of subjects who achieve a \geq 1.5-point reduction in pain rating from baseline to 5+ years post-treatment.
- d) The proportion of patients with surgical interventions for low back pain of the same treatment region post the Intracept procedure.
- e) The proportion of patients currently utilizing opioids for low back pain of the same treatment region.
- f) The proportion of patients utilizing injections in the past 12 months for low back pain of the same treatment region.
- g) Patient satisfaction with the Intracept Procedure.

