#### **4.4.2 Primary Efficacy Analysis**

The efficacy analysis will be conducted all consented treated subjects with a 5+ year study visit. Results will be reported for observed data only; missing values will not be imputed.

The primary analysis will test the mean improvement in ODI from baseline to 5+ years as an intra-patient comparison. The mean change will be analyzed with an ANCOVA with a covariate of baseline ODI score. See Appendix A - Table 8.

If  $p \leq 0.05$  then it may be concluded that a significant functional improvement was demonstrated in axial low back pain subjects treated with the Intracept procedure and that the treatment is durable to mean follow-up for the long term study.

A comparison will be made between the ITT (as treated cohort) and a Intracept only treated cohort (with those subjects that had additional procedures such as RF Ablation, microdiscectomy, fusion, etc. removed).

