**5+ Year Follow-up Study Endpoints:**

Tables 8 and 9 will be performed for both the ITT (as treated) population and the Intracept treated only population.

Table 8 – Primary Endpoint Results	
	SMART 5+ Yr Follow-up Subjects N = XX Mean ± SD (N), Median [Interquartile Range], Range or % (n/N)
Time of Assessment	
Years since Index Procedure	Mean + SD, Median, Range
Percent with at Least 5 years of Follow-up	% (n/N)
ODI	(N=XX)
Baseline ODI Score (Mean + SD, Median, Range)	Mean + SD, Median, Range
5+ Year ODI Score (Mean + SD, Median, Range)	Mean + SD, Median, Range
Mean change in ODI score from baseline to 5+ Years post-treatment	Mean + SD, Median, Range ( p-value )
ODI Responder Rates	
Subjects with ≥ 10-point ODI decrease	% (n/N) ( p-value )
Subjects with ≥ 15-point ODI decrease	% (n/N) ( p-value )
Subjects with ≥ 20-point ODI decrease	% (n/N) ( p-value )
ODI Response Quartiles	
Subjects with ≤ 24% or less decrease	% (n/N)
Subjects with 25-49% decrease	% (n/N)
Subjects with 50-74% decrease	% (n/N)
Subjects with 75-100% decrease	% (n/N)
	(p-value)

	CD_3012_Rev B Five-Plus Year Follow-Up of SMART Trial Statistical Analysis Plan	Date Effective: November 5, 2019 Page 16 of 21
---	--	---

Table 9 – Secondary Endpoints Results	
	SMART 5+ Yr Follow-up Subjects N = XX
10 Point VAS Numeric Pain Scale	
Baseline VAS Score (Mean + SD, Median, Range)	Mean + SD, Median, Range
5+ Year VAS Score (Mean + SD, Median, Range)	Mean + SD, Median, Range
Mean change in VAS score from baseline to 3 months post-treatment	Mean + SD, Median, Range ( p-value )
VAS Responder Rates	
% of subjects with $\geq$ 1.5 Pt VAS decrease	% (n/N) ( p-value )
% of subjects with $\geq$ 2.0 Pt VAS decrease	% (n/N) ( p-value )
VAS Response Quartiles	
Subjects with $\leq$ 24% or less decrease	% (n/N)
Subjects with 25-49% decrease	% (n/N)
Subjects with 50-74% decrease	% (n/N)
Subjects with 75-100% decrease	% (n/N)
	( p-value )

Table 10 – Regression to the Mean Analysis	
	SMART 5+ Yr Follow-up Subjects N = XX
Regression to the Mean	
Average change in ODI in CONTROL group between baseline and 1 year	Mean, N, 95% CI, t-test p (Ho: $\delta=0$ )
Average change in ODI in CONTROL group between baseline and 2 years	Mean, N, 95% CI, t-test p (Ho: $\delta=0$ )

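### Two of the four satisfaction items in SAP Table 16 do not name the Intracept Procedure, so subjects with a later back operation could rate that operation instead.

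*SAP*

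**What the plan says.** Protocol 5.2(g) lists as a secondary endpoint "Patient satisfaction with the Intracept Procedure". Section 4 of the protocol uses the same object for the telephone visit: the research nurse collects "patient satisfaction with the Intracept Procedure". SAP 3.1.2 repeats the endpoint. Protocol 7.3 and SAP 2.5 describe the instrument as short and non-validated, covering improvement, satisfaction with treatment and willingness to repeat it.

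The items appear only in SAP Appendix A, Table 16:

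1. "How do you feel your condition is post the Intracept Procedure"
2. "I am satisfied with the results of my surgery"
3. "All things considered; I would have the surgery again for the same condition"
4. "Were you able to resume the activity level you enjoyed prior to onset of your low back pain"

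On later operations, SAP 4.4.2 defines an Intracept-only cohort, with "those subjects that had additional procedures such as RF Ablation, microdiscectomy, fusion, etc. removed". Table 13 tabulates such operations by type. Appendix A then states that "Tables 8 and 9 will be performed for both the ITT (as treated) population and the Intracept treated only population". Table 16 is not in that list, and SAP 4.4.3.5 plans only a descriptive summary of the survey.

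**The concern.** The endpoint has a specific object, the Intracept Procedure. The two items that carry satisfaction and willingness to repeat have an unspecified one. For a subject whose only back operation was Intracept, the difference is harmless. For a subject who later had a fusion or discectomy, the word surgery can refer to either operation, and the later one is more recent at a call made more than five years after Intracept.

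The protocol's own usage adds to the ambiguity: in sections 4 and 7.5, surgical interventions are the operations that come after Intracept. The synopsis and section 4 also list those interventions before satisfaction. If the call follows that order, the subject will just have reported the later operation.

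At stake is what the two reported percentages mean. A subject who did poorly after Intracept and well after a fusion could be counted as satisfied and willing to repeat. A subject content with Intracept but unhappy with a later operation could be counted as dissatisfied. The follow-up has no control arm that would share the error.

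**Working it through.** The plan states no figure on this point, so there is none to reproduce. The check compares wording and then derives a bound.

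**Which items name the procedure (Table 16)**

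| Item | Subject matter | Names Intracept? |
|---|---|---|
| 1 | Change in condition | Yes, as a point in time |
| 2 | Satisfaction | No (my surgery) |
| 3 | Willingness to repeat | No (the surgery) |
| 4 | Return to prior activity | No procedure named |

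Item 1 asks about condition since Intracept. That does not separate the effect of Intracept from that of a later operation. Item 4 refers to no operation, so the ambiguity about which surgery is meant does not arise there. The problem is confined to items 2 and 3.

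**Who can be affected.** Only respondents with a later back procedure. SAP 4.4.2 and Table 13 show that such subjects are expected; neither document gives their number.

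**Bound on the shift.** Let N be the number of respondents, m the number with a later procedure, and f = m/N. For either item, compare the yes count if everyone rates Intracept with the count if some of the m rate the later operation. Each of those m answers can change the count by +1, 0 or −1, and no other answer can change. Hence

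|change in yes rate| ≤ m/N = f.

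More precisely, change = f × (a − b), where a is the share of the m whose answer goes from no to yes and b the share whose answer goes from yes to no. The bound is reached only if a = 1 or b = 1, that is, if every re-treated subject rates the later operation and all of them switch in the same direction.

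**Numbers.** f is an assumption, taken as 5% to 20%.

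- f = 0.05: at most 5 percentage points. If all 133 eligible subjects responded, 0.05 × 133 = 6.65, about 7 subjects.
- f = 0.20: at most 20 percentage points; 0.20 × 133 = 26.6, about 27 subjects.
- With a net switch of half (a − b = 0.5, also assumed), the shift is 0.05 × 0.5 = 2.5 points to 0.20 × 0.5 = 10 points. With a − b = −0.5 it has the same size and the opposite sign.

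**Whether a planned output deals with it.** Table 13 will report how many subjects had a procedure, and so will supply f and cap the error. No planned table crosses that information with the satisfaction answers, and the Intracept-only repeat is limited to Tables 8 and 9.

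**The case against.** The best counter-argument is that Table 16 is a table shell, not the questionnaire. The worksheet from which the nurse reads is not in the documents, and it may name the procedure. There is a sign that the shell and the descriptive text are not both verbatim: Protocol 7.3 and SAP 2.5 describe repeating treatment for the same outcome, while item 3 refers to the same condition. This stands, and it makes the rewording conditional on what the worksheet says. It does not remove the point, because Table 16 holds the only wording given and no interviewer instruction defines the term.

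Second, context may resolve the ambiguity. Item 1 names Intracept just before item 2, the whole call is presented as follow-up of Intracept, and the parent trial has Surgical in its title. Many respondents may well understand the items as intended. This lowers the likely error but does not exclude it for someone with a later fusion.

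Third, the endpoint is modest. It is last in the protocol's list, descriptive, measured with an openly non-validated questionnaire, and not part of the composite success definition. That stands, and the point should be weighted accordingly.

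A reader might also infer that the satisfaction rate is bound to be inflated. The documents do not support that. The shift can run either way, and SAP 2.6 allows for later procedures unrelated to the pain Intracept was meant to treat, so a later operation does not in itself mean that Intracept failed.

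**Conclusion.** The point holds as a wording defect with limited reach. Items 2 and 3 of Table 16 do not identify the procedure that the endpoint is about, and subjects with a later back operation could answer about that operation. Each yes rate could move in either direction by at most the share of respondents with a later procedure: 5 to 20 percentage points for an assumed share of 5–20%, and less unless all those subjects switch the same way. This assumes that the worksheet matches Table 16.

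A reader might go further and call satisfaction a headline result that has become uninterpretable. The documents do not bear that out: it is a secondary descriptive endpoint, no test or success claim depends on it, item 1 does mention Intracept, and answers from subjects without a later procedure are not affected. The primary ODI analysis is untouched.

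**What to change.** 1. Compare the worksheet with Table 16. If it uses the same wording and calls are not complete, name the Intracept Procedure in items 2 and 3, on the worksheet and in the table. Because the questionnaire is non-validated, this breaks no established instrument.
2. In any case, also present Table 16 for the Intracept-only cohort already defined in SAP 4.4.2, or split it by whether the subject had a later lumbar procedure. Base the split on any such procedure, not only those adjudicated as treatment failures, since an unrelated operation can be mistaken for the index one just as easily.
3. For answers already collected, state the limit of this remedy: the split gives a clean rate among subjects without a later procedure, but it cannot recover which operation the others rated.

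The cost is IRB handling of the revised wording and one additional table, in which the re-treated group may be small and its percentages imprecise. The procedure data needed for the split are already collected under Protocol 7.5, so no extra visit is required.
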